5.2 Prohibited Interventions

Medications listed below will be prohibited during treatment period.

Concomitant Drug Class: Drug Name	Effect on Concentration	Clinical Comment
Antiarrhythmics: amiodarone	Effect on amiodarone, ledipasvir, and sofosbuvir concentrations unknown	Coadministration of amiodarone with HARVONI may result in serious symptomatic bradycardia. The mechanism of this effect is unknown. Coadministration of amiodarone with HARVONI is not recommended;
Anticonvulsants: carbamazepine phenytoin phenobarbital oxcarbazepine	Decreases ledipasvir Decreases sofosbuvir Decreases GS-331007	Coadministration of HARVONI with carbamazepine, phenytoin, phenobarbital, or oxcarbazepine is expected to decrease the concentration of ledipasvir and sofosbuvir, leading to reduced therapeutic effect of HARVONI. Coadministration is not recommended.
Antimycobacterials: Rifabutin Rifampin Rifapentine	Decreases sofosbuvir Decreases GS-331007	Coadministration of HARVONI with rifabutin or rifapentine is expected to decrease the concentration of sofosbuvir, leading to reduced therapeutic effect of HARVONI. Coadministration is not recommended Coadministration of HARVONI with rifampin, an intestinal P-gp inducer, is not recommended
Herbal supplements: St. John's wort (Hypericum perforatum)	Decreases sofosbuvir Decreases GS-331007	Coadministration of HARVONI with ST. Joh's wort, an intestinal P-gp inducer, is not recommended
HMG-CoA Reductase Inhibitors: Rosuvastatin	Increases rosuvastatin	Coadministration of HARVONI with rosuvastatin may significantly increase the concentration of rosuvastatin which is associated with increased risk of myopathy, including rhabdomyolysis. Coadministration of HARVONI with rosuvastatin is not recommended

5.3 Adherence Assessment

Adherence to study intervention will be assessed at all study visits noted on the Schedule of Evaluations (Section 6.1).

Subjects will have adherence assessed based on medication counts. This will be utilized in a subanalysis to determine if measured adherence rates of < 80% impact clinical outcomes in each Arm.

6. CLINICAL AND LABORATORY EVALUATIONS

6.1 Schedule of Evaluations

	Baseline / Randomi- zation	Days			Week 1	Week 2	Week 4	Week 8	Week 12	Week 16	Week 20	Week 24	Week 32	Week 36	End of Study
		1	2	4	7	14	28 (+/-5 days)	56 (+/-5 days)	84 (+/-5 days)	112 (+/-5 days)		168 (+/-5 days)		252 (+/-5 days)	
Day Post-Randomization	0														
Informed Consent Obtained	X														
Randomization	X														
Review of Inclusion and Exclusion Criteria	X														
Medical History	X														
Liver Transplant Recipient	X														
Liver Transplant Donor	X														
Vital Signs	X						O	O	O	O		O		O	
Laboratory Assessments	X						X	X	X	O		O		O	
Hepatitis C Viral Load Test (HCV PCR RNA)	X						X	X	X	X		X		X	
EKG	X													X	
Review of Immunosuppressants	X						X	X	X	X		X		X	
Viral Substitutions	X						O	O	O	O		O		O	
Pregnancy Test (within 48 hrs of randomization)	X														
Review of Prohibited Medications	X						X	X	X						
Study Drug Compliance							X	X	X						
Virologic Failure															X
Liver Allograft Biopsy							O	O	O	O		O		O	
Fibro Scan	O						O	O	O						
Adverse Events	X						X	X	X	X		X		X	
End of Study															X

X=required; O=optional

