3. STUDY DESIGN

Multi-center, prospective, randomized, open-label, pilot study

ARM 1: LDV/SOF x 12 weeks

ARM 2: LDV/SOF + RBV x 12 weeks

Number subjects:

Multi-center

50 subjects, with 25 subjects in each arm

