4. SELECTION AND ENROLLMENT OF SUBJECTS

4.1 Inclusion Criteria

- a. At least 18 years of age
- b. Signed informed consent
- c. History of HCV genotype 1 or 4
- d. No clinically significant abnormalities or changes on EKG
- e. Randomization post orthotopic liver transplant
- f. Detectable HCV RNA at baseline
- g. Creatinine Clearance of at least 40ml/min using the Cockcroft Gault equation
- h. Negative pregnancy test for female subjects of child bearing potential within 48 hours of randomization

Subjects of reproductive potential agree to use (or have their partner use) two effective contraception methods through 6 weeks following completion of intervention. Subjects who are not of reproductive potential, not sexually active, whose current partner(s) is not of reproductive potential, or whose sexual activity is exclusively homosexual are eligible without requiring the use of contraception.

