6.2 Timing of Evaluations

6.2.1 Pre-Randomization Evaluations

These evaluations occur prior to the subject receiving any study interventions.

Baseline

The evaluations listed under the Baseline visit may be performed up to 14 days prior to randomization, with the exception of the pregnancy test, which must be performed within 48 hours of randomization. Additionally, HCV PCRs may be performed up to 30 days prior to randomization, provided that it was performed after the liver transplant.

Once the subject has been successfully screened and accepted for randomization, randomization must be complete within 48 hours. All subjects randomized will be included in the intent-to-treat analysis.

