6.2.2 Intervention and Evaluations

Once the subject has been successfully randomized, the intervention should be initiated upon that day, but must be initiated within 5 days in case of extenuating circumstances.

Study evaluations must take place within the time window indicated on the Schedule of Evaluations (Section 6.1).

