8. CRITERIA FOR INTERVENTION DISCONTINUATION

The intervention will be withheld/discontinued for specific grades of adverse effects as detailed in section 7. Additionally, the intervention will be discontinued if the subject meets criteria for the following reasons:

Virologic failure, defined as:

Breakthrough: HCV RNA \geq LLOQ after having previously had HCV RNA $<$ LLOQ, while on treatment, confirmed with 2 consecutive values (note: second confirmation value can be posttreatment), or last available on-treatment measurement with no subsequent follow up values, OR

Rebound: > 1 log₁₀IU/mL increase in HCV RNA from nadir while on treatment, confirmed with 2 consecutive values (note: second confirmation value can be post-treatment), or last available on-treatment measurement with no subsequent follow up values, OR

Nonresponse: HCV RNA persistently \geq LLOQ through 8 weeks of treatment, OR

Relapse: HCV RNA \geq LLOQ during the posttreatment period having achieved HCV RNA $<$ LLOQ at end of treatment, confirmed with 2 consecutive values or last available posttreatment measurement

Pregnancy: If a woman becomes pregnant or a male's female partner becomes pregnant while on-study, the subject will be required to instruct investigators immediately. If he/she is in Arm 1, he/she may remain on therapy but will be ineligible for treatment with ribavirin in the event of virologic failure. If he/she is in Arm 2, therapy must be discontinued immediately and the subject will be counseled on the potential risks of exposure by the PI or designee. A discussion will occur with the medical monitor to decide whether the subject is eligible to be continued on sofosbuvir/ledipasvir alone.

Loss of graft: Defined as death or need for retransplant. Patients will be deemed a treatment failure and the intervention will be discontinued.

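### Pregnancy stops Arm 2 therapy at once, yet no pregnancy test is scheduled during the 12 weeks of ribavirin, so detection in female subjects rests on self-report

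*Combined protocol and SAP*

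**What the plan says.** Section 3 sets the ribavirin arm as "ARM 2: LDV/SOF + RBV x 12 weeks".

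Section 8 covers pregnancy in a female subject or in a male subject's partner. In either case "the subject will be required to instruct investigators immediately". For the ribavirin arm the consequence is strict: "If he/she is in Arm 2, therapy must be discontinued immediately". The subject is then counseled on the risks of exposure, and "A discussion will occur with the medical monitor to decide whether the subject is eligible to be continued on sofosbuvir/ledipasvir alone". An Arm 1 subject may stay on therapy but can no longer be given ribavirin after virologic failure.

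Testing is described in three places, and all three describe one test:

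- Section 4.1, item h, as an entry criterion: "Negative pregnancy test for female subjects of child bearing potential within 48 hours of randomization".
- Section 6.2.1, which allows baseline evaluations up to 14 days before randomization, "with the exception of the pregnancy test, which must be performed within 48 hours of randomization".
- Section 6.1, where the row "Pregnancy Test (within 48 hrs of randomization" has a mark in the Baseline / Randomization column and nowhere else, neither required nor optional.

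Section 6.2.2 expects treatment to start on the day of randomization, but allows that it "must be initiated within 5 days in case of extenuating circumstances".

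**The concern.** The stopping rule is absolute, but nothing scheduled on treatment would set it off. A subject can report a pregnancy only once she knows of it. Until then the rule cannot act, and a fully compliant site would go on dispensing ribavirin.

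The protocol itself treats the exposure as serious. It excludes pregnant women and men with pregnant partners (Section 4.2), requires two contraceptive methods until 6 weeks after treatment (Section 4.1), and calls for an immediate stop with counseling (Section 8). The first two measures lower the chance of an exposed pregnancy, but neither detects one.

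The other stopping rules have data behind them. Virologic failure is judged on HCV RNA, which is required at Weeks 4, 8 and 12. The ribavirin dose rules in Section 5.1 depend on hemoglobin, white cells, platelets and eGFR, and laboratory assessments are required at those same visits. Pregnancy, which calls for the fastest action, has no scheduled on-treatment measurement.

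**Working it through.** The plan gives no figure of its own on this point. The check sets the sections side by side and counts days.

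**Inputs**

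- Ribavirin course: 12 weeks (Section 3), so 12 × 7 = 84 days.
- Pregnancy tests: one, no more than 48 hours (2 days) from randomization (Sections 4.1, 6.1, 6.2.1).
- Latest start of treatment: 5 days after randomization (Section 6.2.2).
- Visits, ±5 days (Section 6.1): Week 4 = day 28, window 23 to 33; Week 8 = day 56, window 51 to 61; Week 12 = day 84, window 79 to 89.
- Arm 2 size: 25 (Section 3).
- Share of women of childbearing potential: not stated. Assumed range 0 to 20%.

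**Is a test required anywhere else?** Section 7 (adverse events) and Section 9.7 (safety) add none. The laboratory assessments at Weeks 4, 8 and 12 are not itemized, but the pregnancy test has a separate row marked at baseline only, so nothing shows that it is included. The blank cells are unlikely to be a fault in reading the table: the row label itself limits the test to the time of randomization, the other two sections agree, and neighboring rows keep their later marks.

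**As written**

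- Required tests during ribavirin: 0 in 84 days.
- Longest time from the only test to the end of the course: 2 + 5 + 84 = 91 days.
- Age of the test at first dose: at most 2 days on a same-day start; up to 2 + 5 = 7 days on a delayed start.

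**With tests at Weeks 4, 8 and 12**

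- First dose (day 0) to Week 4: at most 33 days.
- Week 4 to Week 8: at most 61 − 23 = 38 days.
- Week 8 to the end of dosing: at most 84 − 51 = 33 days for a day-0 start, or 89 − 51 = 38 days for a day-5 start.
- Longest untested stretch on drug: 28 days nominally, 38 at most, against 84 now.
- Planned ribavirin still avoidable when a test is positive (nominal days): 84 − 28 = 56 at Week 4, 84 − 56 = 28 at Week 8, and 84 − 84 = 0 at Week 12.

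**Number of tests**

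- Arm 2, three visits: 25 × (0 to 0.20) × 3 = 0 to 15 tests, in 0 to 5 women.
- Both arms, with a fourth test at Week 16: 50 × (0 to 0.20) × 4 = 0 to 40 tests.

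**The case against.** The facts are hard to dispute, so the case against concerns weight and scope.

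- **Subjects are seen about every 28 days.** Adverse events are reviewed at Weeks 4, 8 and 12, and blood is drawn, so there are occasions to ask about pregnancy and to test on suspicion. This stands as an additional safeguard. It does not close the gap, because the review still depends largely on what the subject knows and says, and no test is required.
- **The group may be empty.** Eligibility sets only a minimum age, and the 0 to 20% range is an assumption. Harm would also need two contraceptive methods to fail and the pregnancy to go unrecognized, and no probability can be put on either from the documents. That is fair: expected harm cannot be quantified. The cost falls with the number of women, however, and is only a wording change if there are none.
- **The remedy is partial.** An undetected exposure of up to 38 days remains possible, the Week 12 test comes too late to spare ribavirin, and 84 days is itself a maximum because ribavirin may stop early for toxicity. All of this stands. The Week 4 and Week 8 tests are the ones that matter for the stopping rule.
- **The first-dose point is minor.** It is: the delay is reserved for exceptional circumstances and adds at most 5 days to the age of the test.
- **Testing may be required elsewhere.** Section 10.3 mentions a manual of procedures that is not among the documents, and the consent pages were not available. The finding is therefore limited to the visible text, although a dedicated baseline-only row makes hidden testing unlikely.
- **The rule and the schedule do not contradict each other.** True: the stop works for any pregnancy that is reported. The concern is with those that are not yet recognized.

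**Conclusion.** The concern holds. In the protocol as written, a woman in Arm 2 may take ribavirin for up to 84 days with no required pregnancy test, and the immediate-stop rule depends on her recognizing and reporting the pregnancy. Testing at existing visits would bring the longest untested stretch down to 28 days nominally and 38 at most.

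This is a gap in safety monitoring, probably affecting few subjects and at low probability, but with a serious consequence and a cheap remedy. The change should be made. The conclusion rests on the visible text of the protocol; the number of women affected rests on the assumed 0 to 20%. The delayed-start point is secondary. Estimation of SVR12, the sample size and the intent-to-treat analysis are not affected.

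**What to change.** 1. In Section 6.1, mark a urine pregnancy test at Weeks 4, 8 and 12 for women of childbearing potential, in Arm 2 at minimum. Weeks 4 and 8 can trigger the Section 8 stop; Week 12 mainly records status at the end of dosing. Extending this to Arm 1 has some value, because Section 8 bars ribavirin after virologic failure in a pregnant Arm 1 subject and Section 6.2.3 offers reimbursed ribavirin in that setting.
2. In Sections 4.1 (item h), 6.1 and 6.2.1, require a negative result in the 48 hours before first dose, repeated only if a delayed start takes the test past that limit. On a same-day start the eligibility test serves both purposes.
3. Optionally, add a test at Week 16, which falls inside the 6-week contraception period.

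Section 8 needs no change: the medical-monitor step stays, and Arm 1 subjects may still remain on therapy.

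The cost is a wording amendment plus the tests counted above: 0 to 15 in Arm 2 for the minimum version, and up to 40 with both arms and Week 16, all at visits already scheduled. Item 2 adds a test only when the start is delayed. Pregnancies in male subjects' partners would still be found only by report.

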6.2 Timing of Evaluations

6.2.1 Pre-Randomization Evaluations

These evaluations occur prior to the subject receiving any study interventions.

Baseline

The evaluations listed under the Baseline visit may be performed up to 14 days prior to randomization, with the exception of the pregnancy test, which must be performed within 48 hours of randomization. Additionally, HCV PCRs may be performed up to 30 days prior to randomization, provided that it was performed after the liver transplant.

Once the subject has been successfully screened and accepted for randomization, randomization must be complete within 48 hours. All subjects randomized will be included in the intent-to-treat analysis.

6.2.2 Intervention and Evaluations

Once the subject has been successfully randomized, the intervention should be initiated upon that day, but must be initiated within 5 days in case of extenuating circumstances.

Study evaluations must take place within the time window indicated on the Schedule of Evaluations (Section 6.1).

6.2.3 Intervention Discontinuation Evaluations

At the scheduled time of intervention discontinuation (EOT, last date of study medication), the following evaluations must be completed: HCV PCR and HCV viral substitutions (in the event of virologic failure)

If a subject prematurely terminates study intervention, a visit will be scheduled with the Principal-Investigator (PI) or designee within 72 hours to evaluate the reason for early termination. The PI or designee will attempt to resolve any issues leading to early termination and encourage the subject to resume study intervention as soon as possible. It will be clarified whether they are terminating from all components of the trial or only from the primary intervention component of the trial. If possible, the subjects will be encouraged to continue to be followed and evaluated according to the Schedule of Evaluations (Section 6.1) even if they no longer wish to receive study treatment.

Subjects that discontinue intervention due to virologic failure will be withdrawn from the study and deemed a treatment failure. These subjects may receive alternative treatment at

the investigator's discretion. SOF/LDV will be supplied upon request and RBV will be reimbursed by Gilead Sciences, Inc for up to 24 weeks if requested.

7. MANAGEMENT OF COMMON OR EXPECTED ADVERSE EXPERIENCES

The severity of adverse events will be determined using the grading system outlined in the NCI Common Terminology Criteria for Adverse Events Version 4.03 (CTCAE), as it best fits the diagnostic terminology used in naming the event at the site clinical level.

SOFOBUVIR/LEDIPASVIR OR RIBAVIRIN (ADVERSE EVENTS IN COMMON)

CTCAE SOC	Adverse Event	Grade Description	Criteria for Modification of Intervention	Procedure for Modification
General disorders and administration site conditions	Fatigue	1 – Relieved by rest	Grade 3 or if requested by study participant	Intervention can be withheld for up to 5 days. If there is no resolution, the case will be discussed with the medical monitor and the intervention may be discontinued.
		2 – Not relieved by rest; limiting instrumental ADL		
		3 – Not relieved by rest; limiting self-care ADL		
Nervous system disorders	Headache	1 – Mild pain	Grade 3 or if requested by study participant	Intervention can be withheld for up to 5 days. If there is no resolution, the case will be discussed with the medical monitor and the intervention may be discontinued.
		2 – Moderate pain; limiting instrumental ADL		
		3 – Severe pain; limiting self-care ADL		
Gastrointestinal disorders	Nausea	1 – Loss of appetite without alteration in eating habits	Grade 3 or if requested by study participant	Intervention can be withheld for up to 5 days. If there is no resolution, the case will be discussed with the medical monitor and the intervention may be discontinued.
		2 – Oral intake decreased without significant weight loss, dehydration or malnutrition		
		3 – Inadequate oral caloric or fluid intake; tube feeding, TPN, or hospitalization indicated		
Gastrointestinal disorders	Vomiting	1 – 1-2 episodes (separated by 5 minutes) in 24 hours	Grade 3 or if requested by study participant	Intervention can be withheld for up to 5 days. If there is no resolution, the case will be discussed with the medical monitor and the intervention may be discontinued.
		2 – 3-5 episodes (separated by 5 min) in 24 hours		

		3 - ≥ 6 episodes (separated by 5 min); tube feeding, TPN or hospitalization indicated		
Gastrointestinal disorders	Diarrhea	1 - Increase of < 4 stools per day over baseline; mild increase in ostomy output compared to baseline	Grade 3 if requested by study participant, treatment-resistant or recurrent; Grade 4 or 5	Intervention can be withheld for up to 5 days. If there is no resolution, the case will be discussed with the medical monitor and the intervention may be discontinued. Grade 5: Intervention will be permanently discontinued
		2 - Increase of 4-6 stools per day over baseline; moderate increase in ostomy output compared to baseline		
		3 - Increase of ≥ 7 stools per day over baseline; incontinence; hospitalization indicated; severe increase in ostomy output compared to baseline; limiting self care ADL		
		4 - Life-threatening consequences; urgent intervention indicated		
		5 - Death		
Psychiatric disorders	Insomnia	1 - Mild difficulty falling asleep, staying asleep or waking up early	If requested by study participant	Intervention can be withheld for up to 5 days. If there is no resolution, the case will be discussed with the medical monitor and the intervention may be discontinued.
		2 - Moderate difficulty falling asleep, staying asleep or waking up early		
		3 - Severe difficulty in falling asleep, staying asleep or waking up early		
Musculoskeletal and connective tissue disorders	Arthralgia	1 - Mild pain	Grade 3 or if requested by study participant	Intervention can be withheld for up to 5 days. If there is no resolution, the case will be discussed with the medical monitor and the intervention may be discontinued.
		2 - Moderate pain; limiting instrumental ADL		
		3 - Severe pain; limiting self care ADL		

Renal and urinary disorders	Chronic kidney disease	1 - CrCl < LLN-60ml/min/1.73m ² ; proteinuria 2+ present; urine protein/creatinine > 0.5	Grade 2	Sofosbuvir/Ledipasvir to be held if CrCl <40ml/min/1.73m ² . Intervention can be withheld for up to 5 days. If there is no resolution, the case will be discussed with the medical monitor and the intervention may be discontinued. Ribavirin dose should be reduced to alternating doses of 200mg and 400mg every other day if CrCl 30-50ml/min/1.73m ² Interventions can be withheld for up to 5 days. If there is no resolution, the case will be discussed with the medical monitor and the intervention may be discontinued. Grade 5: Intervention will be permanently discontinued
		2 - CrCl 59-30m/min/1.73m ²		
		3 - CrCl 29-15ml/min/1.73m ²	Grade 3-5	
		4 - < 15ml/min/1.73m ² ; dialysis indicated		
		5 - Death		
Investigations	Blood bilirubin increased	1 - >ULN - 1.5x ULN	Grade 3-4	Intervention can be withheld for up to 5 days. If there is no resolution, the case will be discussed with the medical monitor and the intervention may be discontinued.
		2 - >1.5-3x ULN		
		3 - >3-10x ULN		
		4 - >10x ULN		
Investigations	Lipase increased	1 - > ULN-1.5x ULN	Grade 3-4	Intervention can be withheld for up to 5 days. If there is no resolution, the case will be discussed with the medical monitor and the intervention may be discontinued.
		2 - >1.5-2x ULN		
		3 - >2-5x ULN		
		4 - >5x ULN		

Ribavirin

CTCAE SOC	Adverse Event	Grade Description	Criteria for Modification of Intervention	Procedure for Modification
Blood and lymphatic system disorders	Anemia	1 - Hgb <LLN-10g/dL	Grade 2, modifications to dosage	Grade 2: see dosage adjustment procedure in section 5.1.iii
		2 - Hgb <10-8g/dL		
		3 - < 8g/dL	Grade 3-5: permanently discontinue ribavirin	Grade 3-5: ribavirin will be permanently discontinued. Subject experiencing Grade 3 or 4 will continue the study intervention and follow study
		4 - Life-threatening consequences; urgent intervention indicated		

		5 – Death		evaluations as detailed in section 6.1
Blood and lymphatic system disorders	Hemolysis	1 – Laboratory evidence of hemolysis only (e.g. DAT, Coombs', schistocytes, decreased haptoglobin)	Grade 2: modifications to dosage Grade 3-5: permanently discontinued	Grade 2: see dosage adjustment procedure in section 5.1.iii Grade 3-5: intervention will be permanently discontinued.
		2 – Evidence of hemolysis and $\geq 2g/dL$ decrease in Hgb		
		3 – Transfusion or medical intervention indicated		
		4 – Life-threatening consequences; urgent intervention indicated		
		5 – Death		
Hepatobiliary disorders	Hepatic failure	3 – Asterixis; mild encephalopathy; limiting self care ADL	Grade 3-5	Intervention can be withheld for up to 5 days. If there is no resolution, the case will be discussed with the medical monitor and the intervention may be discontinued. Grade 5: Intervention will be permanently discontinued
		4 – Moderate to severe encephalopathy; coma; life-threatening consequences		
		5 – Death		
Immune system disorders	Allergic reaction	1 – Transient flushing or rash, drug fever < 38 degrees C; intervention not indicated	Grade 3-5 or if requested by study participant	Intervention can be withheld for up to 5 days. If there is no resolution, the case will be discussed with the medical monitor and the intervention may be discontinued. Grade 5: Intervention will be permanently discontinued
		2 – Intervention indicated; responds promptly to symptomatic treatment; prophylactic medications indicated for ≤ 24 hours		
		3 – Prolonged (not rapidly responsive to symptomatic medication); recurrence of symptoms following initial improvement; hospitalization indicated for clinical sequelae		

		4 – Life-threatening consequences; urgent intervention indicated		
		5 - Death		
Immune system disorders	Anaphylaxis	3 – Symptomatic bronchospasm, with or without urticarial; parenteral intervention indicated; allergy-related edema/angioedema; hypotension	Grade 3-5	Intervention can be withheld for up to 5 days. If there is no resolution, the case will be discussed with the medical monitor and the intervention may be discontinued. Grade 5: Intervention will be permanently discontinued
		4 – Life-threatening consequences; urgent intervention indicated		
		5 – Death		
Gastrointestinal disorders	Pancreatitis	2 – Enzyme elevation or radiologic findings only	Grade 3-5	Intervention can be withheld for up to 5 days. If there is no resolution, the case will be discussed with the medical monitor and the intervention may be discontinued. Grade 5: Intervention will be permanently discontinued
		3 – Severe pain; vomiting; medical intervention indicated (e.g. analgesia, nutritional support)		
		4 – Life-threatening consequences; urgent intervention indicated		
		5 – Death		
General disorders and administration site conditions	Irritability	1 – Mild; easily consolable	Grade 3 or if requested by study participant	Intervention can be withheld for up to 5 days. If there is no resolution, the case will be discussed with the medical monitor and the intervention may be discontinued.
		2 – Moderate; limiting instrumental ADL; increased attention indicated		
		3 – Severe abnormal or excessive response; limiting self care ADL; inconsolable		
Skin and subcutaneous tissue disorders	Pruritis	1 – Mild or localized; topical intervention indicated	Grade 3 or if requested by study participant	Intervention can be withheld for up to 5 days. If there is no resolution, the case will be

		2 – Intense or wide-spread; intermittent; skin changes from scratching (e.g. edema, papulation, excoriations, lichenification, oozing/crusts); oral intervention indicated; limiting instrumental ADL		discussed with the medical monitor and the intervention may be discontinued.
		3 – Intense or wide-spread; constant; limiting self care ADL or sleep; oral corticosteroid or immunosuppressive therapy indicated		
Respiratory, thoracic and mediastinal disorders	Dyspnea	1 – Shortness of breath with moderate exertion	Grade 3-5 or if requested by study participant	Intervention can be withheld for up to 5 days. If there is no resolution, the case will be discussed with the medical monitor and the intervention may be discontinued. Grade 5: Intervention will be permanently discontinued
		2 – Shortness of breath with minimal exertion; limiting instrumental ADL		
		3 – Shortness of breath at rest; limiting self care ADL		
		4 – Life-threatening consequences; urgent intervention indicated		
		5 – Death		
Musculoskeletal and connective tissue disorders	Myalgia	1 – Mild pain	Grade 3 or if requested by study participant	Intervention can be withheld for up to 5 days. If there is no resolution, the case will be discussed with the medical monitor and the intervention may be discontinued.
		2 – Moderate pain; limiting instrumental ADL		
		3 – Severe pain; limiting self care ADL		
Investigations	Neutrophil count decreased	1 - <LLN-1500/mm3	Grade 3-4	Intervention can be withheld for up to 5 days. If there is no resolution, the case will be discussed with the medical monitor and the intervention may be discontinued.
		2 - <1500-1000/mm3		
		3 - <1000-500/mm3		
		4 - <500/mm3		
Psychiatric disorders	Depression	1 – Mild depressive symptoms	Grade 3-5 or if requested by study participant	Intervention can be withheld for up to 5 days. If there is no resolution, the case will be discussed with the medical monitor and the intervention
		2 – Moderate depressive symptoms; limiting instrumental ADL		

		3 – Severe depressive symptoms; limiting self care ADL; hospitalization not indicated		may be discontinued.
		4 – Life-threatening consequences; threats of harm to self or others; hospitalization indicated		Grade 5: Intervention will be permanently discontinued
		5 – Death		

Transplant and Immunosuppression-related

CTCAE SOC	Adverse Event	Grade Description	Criteria for Modification of Intervention	Procedure for Modification
Infections and infestations	Abdominal infection	3 – IV antibiotic, antifungal, or antiviral intervention indicate; radiologic or operative intervention indicated	Grade 4-5	Grade 4: Intervention can be withheld for up to 5 days. If there is no resolution, the case will be discussed with the medical monitor and the intervention may be discontinued. Grade 5: Intervention will be permanently discontinued
		4 – Life-threatening consequences; urgent intervention indicated		
		5 – Death		
Infections and infestations	Biliary tract infection	3 – IV antibiotic, antifungal, or antiviral intervention indicate; radiologic or operative intervention indicated	Grade 4-5	Grade 4: Intervention can be withheld for up to 5 days. If there is no resolution, the case will be discussed with the medical monitor and the intervention may be discontinued. Grade 5: Intervention will be permanently discontinued
		4 – Life-threatening consequences; urgent intervention indicated		
		5 – Death		
Infections and infestations	Hepatic infection	3 – IV antibiotic, antifungal, or antiviral intervention indicate; radiologic or operative intervention indicated	Grade 4-5	Grade 4: Intervention can be withheld for up to 5 days. If there is no resolution, the case will be discussed with the medical monitor and the intervention may be discontinued. Grade 5: Intervention will be permanently discontinued
		4 – Life-threatening consequences; urgent intervention indicated		
		5 – Death		

Infections and infestations	CMV	1 – Isolation of CMV from blood or sterile site or positive CMV PCR without clinical symptoms	Grade 4-5	Grade 4: Intervention can be withheld for up to 5 days. If there is no resolution, the case will be discussed with the medical monitor and the intervention may be discontinued. Grade 5: Intervention will be permanently discontinued
		2 – Isolation of CMV from blood or sterile site or positive CMV PCR with clinical symptoms (fever, malaise, leukopenia, thrombocytopenia)		
		3 - Isolation of CMV from blood or sterile site or positive CMV PCR with clinical symptoms (fever, malaise, leukopenia, thrombocytopenia) and histological evidence of viral cytopathic effect or positive CMV culture from a deep tissue specimen		
		4 – Life-threatening consequences; urgent intervention indicated		
		5 – Death		
Infections and infestations	Wound infection	2 – localized; local intervention indicated (e.g. topical antibiotic, antifungal, antiviral)	Grade 4-5	Grade 4: Intervention can be withheld for up to 5 days. If there is no resolution, the case will be discussed with the medical monitor and the intervention may be discontinued. Grade 5: Intervention will be permanently discontinued
		3 – IV antibiotic, antifungal, or antiviral intervention indicated; radiologic or operative intervention indicated		
		4 – Life-threatening consequences; urgent intervention indicated		
		6 – Death		

